10.12 Appendix 12: Quantitative Myasthenia Gravis Scale

This document contains confidential information and is intended for use only in the application of the product.

[figure not shown]
Confidential
Authorization

Quantitative MG Testing

[figure not shown]
[REDACTED]

[REDACTED]

This document cannot be used to support any marketing authorization application and any extension or variations thereof.

[figure not shown]

PUBLIC COPY
This document cannot be used to support any marketing authorization application and any extensions or variations thereof.

[figure not shown]
This document is confidential and intended solely for the individual named.

of. Authorization

[figure not shown]
This document is

Confidential
of.
Authorization

[figure not shown]
This document is

Confidential
Authorization

[figure not shown]
This document is

Confidential

This document is confidential and intended solely for the individual named. Any distribution or disclosure of this information is strictly prohibited.

ization

[figure not shown]

This

[figure not shown]
of.
Authorization

10.13 Appendix 13: Myasthenia Gravis-Composite scale

[figure not shown]
Study: MG0003	Visit: _____	Visit Date: 

 	 	 	 	 	

DD	MM	MM	YY	YY	

						DD	MM	MM	YY	YY	Subject No.: 

 	 	 	 	 	 	 	 	

									Page 1 of 1
DD	MM	MM	YY	YY																		

[figure not shown]

10.14 Appendix 14: Myasthenia Gravis-Activities of Daily Living

[figure not shown]

10.15 Appendix 15 Myasthenia Gravis Symptoms PRO

[figure not shown]

This

[figure not shown]

10.16 Appendix 16: 5-Level European quality of life 5 dimensions

authorization
thereof.

[figure not shown]
This docu

This doc

[figure not shown]
ation

10.17 Appendix 17: Myasthenia Gravis Impairment Index

MG Impairment Index (MGI)™ - Patient Questionnaire

ID: _____

[figure not shown]

This

[figure not shown]
ization

MG Impairment Index (MGII)TM - Patient Questionnaire

[figure not shown]
ID: _____

[figure not shown]
MG Impairment Index (MGII) - Examination

[figure not shown]
Myasthenia Gravis Impairment Index (MGII) - Examination Manual

Myasthenia Gravis Impairment Index (MGII) - Scoring Sheet

[figure not shown]
10.18 Appendix 18: Revised 15-item myasthenia gravis quality of life questionnaire

[figure not shown]

Authorization
proof.

This document

10.19 Appendix 19: Tuberculosis questionnaire

This document cannot be used to support any marketing authorisation application and any extensions or variations thereof.

PUBLIC COPY

10.20 Appendix 20: Management of headaches, diarrhea, and infections and hypogammaglobulinemia

10.20.1 Management of headache

Based on current available clinical data, headache is the most commonly reported adverse drug reaction in study participants treated with rozanolixizumab. Study participants should be well informed of this potential adverse drug reaction and should be instructed on how to manage it.

Determination of the severity of headache will be consistent with National Cancer Institute Common Terminology Criteria for Adverse Events (CTCAE) version 5.0 (Section 10.3). Severe headache is defined as severe pain limiting self-care activities of daily living (ADL). Self-care activities of daily living (ADL) refers to bathing, dressing and undressing, feeding self, using the toilet, and taking medications.

In the event of headache Investigators will take medical history of previous headaches, concomitant medication, and co-morbidities (eg, asthma) in consideration.

Study participants experiencing severe and/or serious headache will complete the Headache Questionnaire (Section 10.21, Appendix 21) daily until resolving or resolution (ie, if headache becomes nonserious, moderate or mild or completely resolved, whichever comes first). If the severe or serious headache is initially reported at a home visit or during a telephone call, the study participant should be reviewed at the study site as soon as is practically possible for further investigations. Study participants should be monitored for signs and symptoms suggestive of central nervous system involvement and evaluated immediately if other causes (eg, meningitis, intracranial bleeding) are suspected. Further neurological workup may be performed (if indicated) at the discretion of the Investigator or the treating physician and may include, a computed tomography scan, magnetic resonance imaging and/or a lumbar puncture for cerebral spinal fluid collection. In addition, samples for exploratory safety biomarkers should be collected for study participants experiencing severe headache or serious headaches when possible. These investigations will be performed to further understand the mechanism of headaches in the study participants.

Treatments must be permanently discontinued if a study participant has a serious headache that is considered related to the IMP in the opinion of the Investigator. Treatment should be temporarily put on hold if a study participant experiences a severe AE of headache that is considered related to the study medication in the opinion of the Investigator, and is not resolved prior to the next scheduled study treatment. If deemed appropriate by the Investigator and agreed upon by the study participant and the sponsor, the study treatment can resume upon the resolution of the severe headache event. The benefit and risk of the treatment should be carefully considered prior to reinitiating the IMP. However, if a treatment related severe headache reoccurs, the treatment must be permanently discontinued.

Headaches will be treated as clinically indicated according to local guidelines. It is recommended to start the analgesic at early onset of headache. At the discretion of the Investigator, study participants may carry a recommended analgesic with the instruction for frequency and dosage provided. Study participants experiencing any treatment related headache will be followed until resolution of the event.

Prophylactic treatment of headaches may be permitted for study participants who have experienced previous episodes of treatment related moderate or severe headache after discussion with the medical monitor. The benefit risk of continuing treatment with IMP and chronic prophylactic with analgesics must be carefully evaluated by the Investigator.

PUBLIC COPY
This document cannot be used to support any marketing authorization application and any extensions or variations thereof.

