6.6 Dose modification

Study participants will be allowed to switch dose arms for tolerability and efficacy reasons, as well as bodyweight changes at the discretion of the Investigator after the first dose of rozanolixizumab. However, when possible, the dose assigned at randomization should be maintained for at least 6 weeks, unless a dose modification is required earlier for tolerability or efficacy reasons. If a dose adjustment is made, the Investigator should encourage study

participants to stay on the modified dose for at least 6 weeks, unless further dose adjustments or discontinuation of study medication is required for the safety of the study participant.

Study participants who experience any AEs that meet the study medication discontinuation criteria (Section 7.1 and Section 0) should have rozanolixizumab discontinued. Study participants in the [REDACTED] cohort who experience a possibly related toxicity other than those that met the study drug discontinuation criteria as defined in Section 7.1 and Section 0 are allowed to switch to [REDACTED] at the Investigator's discretion. Recommended dose modifications due to toxicities may include (but not exclusive):

- Moderate to severe headaches that are considered to be related to rozanolixizumab (Section 10.20.1)
- Moderate to severe GI disturbances that are considered to be related to rozanolixizumab
- Moderate to severe toxicities (\geq Grade 2 as defined by CTCAE, version 5) for which rozanolixizumab cannot be excluded as a cause
- Recurrent hypogammaglobulinemia with a serum total IgG $<2\text{g/L}$

The date and reason for dose change of rozanolixizumab is to be recorded on each study participant's eCRF.

If any safety concerns are identified in MG0003 (ie, as recommended by the IDMC), or if one of the dose arms is determined to be futile and is discontinued in MG0003, corresponding changes may be made in the MG0004 dosing scheme. A study participant on a dose that was discontinued will switch doses immediately.

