7.1.3 Discontinuation of study medication due to other AEs or medical conditions

A study participant **must** permanently discontinue study medication if any of the following events occur:

1. Study participant develops an illness that would interfere with his or her continued participation.
2. Study participant has new onset or recurrent neoplastic disease (except for superficial basal or squamous cell carcinoma of the skin not requiring targeted biological therapy, chemotherapy or radiation)
3. Study participant has a serious infective episode requiring hospitalization or IV antibiotic therapy (including but not limited to bacteremia or sepsis, meningitis, osteomyelitis or septic arthritis, pneumonia, or visceral abscess).
4. Study participant meets potential drug-induced liver injury (PDILI) permanent discontinuation criteria.
5. Study participant has a TB test that is confirmed positive or any further evidence suggestive of potential TB infection (ie, exposure) and further examinations result in a diagnosis of active TB or latent TB infection (LTBI).
6. If a nontuberculosis mycobacterium infection (NTMB) is identified during a study, the same withdrawal procedures as those used for an active TB infection identified during the study should be followed.
7. Study participant experiences a serious AE of headache which is considered related to the study medication in the opinion of the Investigator.
8. Study participant has an AE of severe or serious infusion or anaphylactic reaction requiring corticosteroid and/or epinephrine therapy (see Section 10.22) (Sampson et al, 2006).

Study participants **may** permanently discontinue study medication at the discretion of the Investigator, Medical Monitor, and Study Physician if any of the following events occur:

9. Study participant is noncompliant with the study procedures or medications in the opinion of the Investigator.
10. Study participant takes prohibited concomitant medications as defined in this protocol.

Investigators should contact the Medical Monitor, whenever possible, to discuss the withdrawal of a participant in advance. Investigators should attempt to obtain information on study participants in the event of withdrawal (eg, reason for withdrawal, any safety information).

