7.1.4 Temporary IMP discontinuation

Study participant ***must be*** TEMPORARILY discontinued from the IMP if any of the following events occur:

1. The study participant develops an event of hypogammaglobulinemia with a serum total IgG of <1g/L irrespective of infection. When the IgG level reaches ≥ 2 g/L, the study participant may be allowed to continue treatment with IMP (see Appendix 22; Section 10.22.3).
2. In the event of confirmed COVID-19 infection. IMP may be restarted if clinically appropriate when signs and symptoms have resolved.

Study participants ***may be TEMPORARILY discontinued from the IMP*** if the following events occur:

1. The study participant develops a non-serious persisting or recurrent infection with serum total IgG level between ≥ 1 and <2g/L. Upon resolution of infection and the IgG returning to level of ≥ 2 g/L, the study participant may be allowed to resume treatment with the IMP (see Appendix 22; Section 10.22.3).
2. In the event of suspected (eg, signs/symptoms such as fever, cough, shortness of breath) COVID-19 infection, or known exposure sufficient to necessitate testing or self-imposed quarantine, IMP may be restarted when clinically appropriate if:
 - a. COVID-19 test is negative, and signs and symptoms have resolved.
 - b. If test is not available, resolution of signs and symptoms and 14 days have passed since initial presentation of the clinical signs/symptoms.
 - c. If asymptomatic, 14 days have passed since known exposure.

The investigator should discuss with sponsor's study physician prior to re-initiating the IMP. As appropriate, virtual assessments could continue (eg, AE collection, PRO assessments).

If IMP treatment is resumed, continue the next dose as previously scheduled. No "make up" dose is permitted. The participant should subsequently follow the visit schedule as described in the protocol and the eCRF should be completed accordingly.

The study participant should follow the visit schedule as described in the protocol and the eCRF completed accordingly.

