10.20.4 Management of infusion reactions or hypersensitivity reactions

Study participants must be closely monitored for reactions during and after the study treatment administration period. Standard precautions must be taken for the study participants with regard to SC infusion complications. Suggested management guidelines for infusion-related reactions and anaphylaxis at the study site are provided in [Table 10-4](#). Definitions of mild, moderate, and severe events will be consistent with CTCAE version 5.0 (Section 10.3). Nurses administering the IMP at home should follow their own management guidelines, which should be reviewed and endorsed by the Investigator prior to first home administration.

Table 10-4: Suggested management guidelines for infusion reactions or anaphylaxis

Type of reaction	Suggested action
Acute – Mild Grade 1	Monitor vital signs every 10 min. If the reaction worsens to Grade 2, follow the instruction below.
Acute – Moderate Grade 2	Interrupt/hold infusion temporarily to further assess and initiate treatment if necessary. Consider the use of IV fluid and antihistamine IV/IM. Consider administering paracetamol or NSAIDs. Monitor vital signs initially every 5 min. If the reaction improves and upon further assessment it is clear that the event is not an anaphylaxis, restart the infusion cautiously. Continue monitor vital signs every 5 minutes. If reaction recurs or worsens to Grade 3, discontinue infusion.
Acute – Severe Grade 3 or anaphylaxis	Discontinue IMP infusion permanently. Alert crash team. Maintain airway; ensure oxygen is available. Administer: 
 – Antihistamine IV/IM, corticosteroids IV, epinephrine IM, and IV fluids as appropriate. – Monitor vital signs every 2 min. – Hospitalize, if condition not improving or worsens – Monitor patient until symptoms resolve.

CTCAE=Common Terminology Criteria for Adverse Events; IM=intramuscular; IMP=investigational medicinal product; IV=intravenous(ly); NSAID=nonsteroidal anti-inflammatory drug

Note: Management criteria were adapted from the CTCAE v5.0 (National Cancer Institute, 2017).

[figure not shown]
Conditions in which anaphylaxis is likely should be diagnosed using Sampson’s Criteria (Sampson et al, 2006) as described in (Appendix 22, Section 10.22). The infusion must be discontinued immediately, and emergency resuscitation measures implemented.

[figure not shown]

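### A recurrent treatment-related severe headache is a mandatory permanent stop in Appendix 20 but not in Section 7.1.3, and Section 6.6 leaves a dose switch open; Grade 3 infusion reactions show a separate, weaker mismatch

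*Protocol*

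**What the plan says.** **Headache.** Protocol Section 10.20.1 has three steps. A serious headache related to study drug ends treatment. For a related severe headache not resolved by the next dose, "Treatment should be temporarily put on hold if a study participant experiences a severe AE of headache"; treatment can resume after resolution if the Investigator, participant and sponsor agree. Then: "if a treatment related severe headache reoccurs, the treatment must be permanently discontinued".

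Section 7.1.3 lists the events for which a participant must "permanently discontinue study medication if any of the following events occur". Its only headache entry is item 7: "Study participant experiences a serious AE of headache which is considered related to the study medication in the opinion of the Investigator". That item does not refer to Section 10.20.1.

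Section 6.6 names "Moderate to severe headaches that are considered to be related to rozanolixizumab" among the toxicities for which a dose modification may be made, with Section 10.20.1 in parentheses beside the entry. The toxicity switch is at the Investigator's discretion and is written for one (redacted) dose cohort. It excludes events meeting the discontinuation criteria of Section 7.1 and of Section 0.

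**Infusion reactions.** Section 7.1.3 item 8 requires a permanent stop for a "severe or serious infusion or anaphylactic reaction requiring corticosteroid and/or epinephrine therapy". Table 10-4 in Section 10.20.4, headed as suggested guidance, says "Discontinue IMP infusion permanently" for a severe Grade 3 reaction or anaphylaxis and sets no condition on the treatment needed.

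**Analysis.** Occurrence of TEAEs leading to permanent withdrawal of study medication is one of two primary safety endpoints (Protocol Section 3; SAP 2.2.1.1). SAP 8.2.2 tabulates TEAEs leading to permanent withdrawal, to temporary withdrawal and to dose change as separate categories.

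**The concern.** A site that works from Section 7.1.3 would not find a recurrent, related, severe but non-serious headache among the mandatory stops. Going on to Section 6.6, it would find related severe headache listed for a possible dose switch, with no distinction between a first and a later episode. A site that works from Appendix 20 would stop treatment. Both could believe that they were following the protocol.

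Section 10.20.1 describes headache as the most commonly reported adverse drug reaction, and severe headache is an adverse event of special monitoring (Section 8.3.7). The action taken decides which SAP category the event enters, including whether it counts toward a primary endpoint. A switch also makes the participant a dose adjuster under SAP 3.6. Because SAP Section 8 summarizes safety by most recent dose unless otherwise specified, later TEAEs then fall in the other dose column. Part of the observed withdrawal rate could thus reflect how sites read the protocol rather than how well the drug is tolerated. There is also a participant-safety interest in giving each event one stated consequence.

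**Working it through.** No arithmetic applies: the documents give no event frequencies and there is no figure to reproduce. The check sets the passages side by side.

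**Step 1: severe is not serious.** Protocol Section 10.3.3 defines severe as an intensity rating and serious by outcome, and says that a severe event may or may not be serious. Item 7 of Section 7.1.3 therefore does not cover a severe, non-serious headache.

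**Step 2: event by event.**

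| Event | Section 7.1.3 | Appendix 20 | Section 6.6 | Result |
|---|---|---|---|---|
| Serious related headache | Must stop (item 7) | Must stop (10.20.1) | Excluded, because Section 7.1 is met | Consistent |
| First severe, non-serious related headache, unresolved by next dose | Not listed | Hold, may resume (10.20.1) | Switch allowed in one cohort | Compatible |
| Recurrent severe, non-serious related headache | Not listed | Must stop (10.20.1) | Entry applies as worded; not excluded by 7.1.3 | Unreconciled |
| Severe infusion reaction needing corticosteroid and/or epinephrine | Must stop (item 8) | Permanent discontinuation (Table 10-4, suggested) | Excluded, because Section 7.1 is met | Consistent |
| Grade 3 infusion reaction not needing either drug | Item 8 not met | Permanent discontinuation (Table 10-4, suggested) | Reached only through the general entry for toxicities of Grade 2 or above | Unreconciled, less firmly |

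**Step 3: does Section 6.6 settle the third row?** Its headache entry points to Section 10.20.1, which favours the Appendix 20 rule. Its exclusion clause, however, names only Section 7.1 and Section 0. No Section 0 exists, so its intended target cannot be recovered, and Appendix 20 is not named. No sentence says which section governs when they differ.

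**Step 4: what counts as recurrence?** The sentence in Section 10.20.1 follows directly after the hold-and-resume sentences. It can mean any second related severe headache, or only one that occurs after treatment was held and restarted. A participant whose first severe headache resolved before the next dose, so that no hold was made, is covered by the first meaning and not by the second.

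**Step 5: the fifth row.** Table 10-4 lists corticosteroids, epinephrine and other treatments to be given as appropriate, so it allows for Grade 3 reactions managed without those two drugs. Its instruction refers to the infusion. Read beside the Grade 2 row, which concerns interrupting and restarting the current infusion, it could mean that infusion or the drug altogether.

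**The case against.** The strongest case on the other side is that the passages can be read together. Section 6.6 is permissive and refers the reader to Section 10.20.1; Section 8.3.7 does the same for headache management. A coherent reading exists: a switch is possible after an earlier episode, and recurrence ends treatment. Section 7.1.3 does not claim to be exhaustive, and the protocol places other stopping rules elsewhere, such as rituximab use in Section 6.5.2 and tuberculosis test results in Section 8.2.6. Severe headache must be reported to the sponsor within 24 hours, and resuming after a hold needs sponsor agreement; both limit divergence between sites.

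Much of this stands. It disposes of several stronger claims that a reader might infer:

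- *That Section 6.6 prescribes a dose change in place of stopping.* It does not. The switch is optional, the toxicity provision covers one cohort, and the entry cites Section 10.20.1.
- *That the headache hold conflicts with Section 7.1.4 because it is absent there.* Section 7.1.4 lists events such as "The study participant develops an event of hypogammaglobulinemia with a serum total IgG of <1g/L irrespective of infection", but it is not a complete list of holds: the pause after IVIg or PEX appears only in Section 6.5.3. This is a matter of placement.
- *That infusion reactions differ in the same way as headache.* They are on the Section 7.1.3 list, with a narrower trigger, and Table 10-4 is only suggested guidance.
- *That every participant with two related severe headaches is affected.* That holds only under the wider meaning of recurrence.
- *That the discrepancy decides the primary endpoint.* The endpoint counts permanent withdrawals for any TEAE, and SAP 4.1 plans no statistical testing.

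What the objection does not remove is the exclusion clause. Omission from Section 7.1.3 alone would be a matter of placement, but Section 6.6 makes placement matter by using Section 7.1 to mark off events for which a switch is not allowed. The coherent reading is available, but it is not stated.

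**Conclusion.** The point holds for headache. Section 10.20.1 makes recurrence of a related severe headache a mandatory permanent stop, Section 7.1.3 omits it, and Section 6.6 does not clearly exclude it from the optional dose switch. The meaning of recurrence is also open. For infusion reactions the point holds only in qualified form: the trigger in Section 7.1.3 is narrower than that in Table 10-4, but the table is suggested guidance and its instruction is ambiguous.

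The consequence is that one event may enter the analysis as a TEAE leading to permanent withdrawal or as a TEAE requiring dose change. How many participants this touches is not known. The upper limit is those with more than one related severe, non-serious headache, plus those with a Grade 3 infusion reaction needing neither corticosteroid nor epinephrine. The effect on the withdrawal endpoint further assumes that sites actually read the sections differently, which sponsor contact may reduce. With descriptive analysis only, no test result is at risk; what is at risk is a consistent meaning for the withdrawal and dose-change counts, and consistent handling of participants. That justifies a correction but does not call the design into question.

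**What to change.** Reconcile Protocol Sections 6.6, 7.1.3, 10.20.1 and Table 10-4 so that each event has one stated consequence, or state which section governs where they differ. In particular:

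- Define recurrence in Section 10.20.1: any second related severe headache, or only one after a hold and restart.
- Make Section 7.1.3 and the Section 6.6 exclusion clause agree with Section 10.20.1, by listing the event or by cross-reference.
- Replace the Section 0 reference in Section 6.6 with its intended target.
- Say whether the Grade 3 instruction in Table 10-4 refers to that infusion or to the drug, and align it with item 8 of Section 7.1.3.

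Which consequence applies to each event is a clinical decision for the sponsor and is not proposed here. The cost is protocol wording; the planned SAP tables need no change.
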